### 3.2.2. Secondary Safety Endpoints

The following endpoints will be described after each vaccination in Groups 1 and 3:

- Percentage of subjects reporting local reactions (pain, redness, and swelling) and by severity within 7 days after each vaccination visit.
- Percentage of subjects reporting systemic events (fever, vomiting, diarrhea, headache, fatigue, chills, muscle pain other than muscle pain at any injection site, and joint pain) and by severity within 7 days after each vaccination visit.
- Percentage of subjects with at least 1 SAE during the following time periods:
  - 30 Days after each vaccination
  - 30 Days after any vaccination
  - During the Stage 1 vaccination phase (from the first study vaccination [Visit 1] through 1 month after the second study vaccination [Visit 4])
  - During the Stage 1 follow-up phase (from 1 month after the second study vaccination [Visit 4] through 6 months after the second study vaccination [Visit 5])
  - Throughout Stage 1 (from the first study vaccination [Visit 1] through 6 months after the second study vaccination [Visit 5])

- Percentage of subjects with at least 1 MAE occurring during the following time periods:
  - 30 Days after each vaccination
  - 30 Days after any vaccination
  - During the Stage 1 vaccination phase (from the first study vaccination [Visit 1] through 1 month after the second study vaccination [Visit 4])
  - During the Stage 1 follow-up phase (from 1 month after the second study vaccination [Visit 4] through 6 months after the second study vaccination [Visit 5])
  - Throughout Stage 1 (from the first study vaccination [Visit 1] through 6 months after the second study vaccination [Visit 5])
- Percentage of subjects with at least 1 NDCMC occurring during the following time periods:
  - 30 Days after each vaccination
  - 30 Days after any vaccination
  - During the Stage 1 vaccination phase (from the first study vaccination [Visit 1] through 1 month after the second study vaccination [Visit 4])
  - During the Stage 1 follow-up phase (from 1 month after the second study vaccination [Visit 4] through 6 months after the second study vaccination [Visit 5])
  - Throughout Stage 1 (from the first study vaccination [Visit 1] through 6 months after the second study vaccination [Visit 5])
- Percentage of subjects with at least 1 AE during the following time periods:
  - 30 Days after each vaccination
  - 30 Days after any vaccination
  - During the Stage 1 vaccination phase (from the first study vaccination [Visit 1] through 1 month after the second study vaccination [Visit 4]).
- Percentage of subjects reporting at least 1 immediate AE after each vaccination.
- The number of days school or work was missed by the subject because of AEs after vaccination.

### 3.3. Other Objectives and Endpoints

#### 3.3.1. Exploratory Objectives and Endpoints

Objective	Endpoint

 
To describe the immune response induced by MenACWY-CRM as measured by hSBA performed with ACWY test strains, 1 month after a booster vaccination in Groups 2 and 4.
 
	
 
Proportion of subjects with hSBA-MenA, hSBA-MenC, hSBA-MenW, and hSBA-MenY titers <math>\geq 1:8</math> (or LLOQ, whichever is higher) at Visit 11, in Groups 2 and 4 separately.
 

 
To describe the immune response induced by bivalent rLP2086 as measured by hSBA performed with 4 primary MenB test strains, measured 1 month after the first vaccination, in the bivalent rLP2086 arms (Group 2 and 4 subjects) combined.
 
	
 
Proportion of subjects who achieve the 5 MenB endpoints at Visit 2.
 
Proportions of subjects with hSBA titers <math>\geq</math> LLOQ, <math>\geq 1:4</math>, <math>\geq 1:8</math>, <math>\geq 1:16</math>, <math>\geq 1:32</math>, <math>\geq 1:64</math>, and <math>\geq 1:128</math> for each of the 4 primary MenB test strains at Visit 2.
 
hSBA GMTs for each of the 4 primary MenB test strains at Visit 2.
 


 
To further describe the immune response induced by MenABCWY compared to the immune response induced by MenACWY-CRM and bivalent rLP2086, as measured by hSBA performed with ACWY test strains and 4 primary MenB test strains, 2 expressing an LP2086 subfamily A protein and 2 expressing an LP2086 subfamily B protein, at blood sampling time points prior to the booster vaccination (Stage 2).
 
	
 
Proportions of subjects with hSBA-MenA, hSBA-MenC, hSBA-MenW, and hSBA-MenY titers <math>\geq 1:8</math>, <math>\geq 1:16</math>, <math>\geq 1:32</math>, <math>\geq 1:64</math>, and <math>\geq 1:128</math> at Visits 7, 8, 9, and 10, in the ACWY-naïve and ACWY-experienced subjects separately.
 
hSBA GMTs for each of the ACWY test strains at Visits 7, 8, 9, and 10, in the ACWY-naïve and ACWY-experienced subjects separately.
 
Proportions of subjects with hSBA titers <math>\geq 1:4</math>, <math>\geq 1:8</math>, <math>\geq 1:16</math>, <math>\geq 1:32</math>, <math>\geq 1:64</math>, and <math>\geq 1:128</math> for each of the 4 primary MenB test strains at Visits 7, 8, 9, and 10, in the ACWY-naïve and ACWY-experienced subjects combined.
 
hSBA GMTs for each of the 4 primary MenB test strains at Visits 7, 8, 9, and 10, in the ACWY-naïve and ACWY-experienced subjects combined.
 


 
To further describe the immune response induced by MenABCWY, as measured by hSBA performed with ACWY and 4 primary MenB test strains, 1 month after a booster vaccination in Groups 1 and 3.
 
	
 
Proportions of subjects with hSBA-MenA, hSBA-MenC, hSBA-MenW, and hSBA-MenY titers <math>\geq 1:8</math>, <math>\geq 1:16</math>, <math>\geq 1:32</math>, <math>\geq 1:64</math>, and <math>\geq 1:128</math> at Visit 11, in Groups 1 and 3 separately.
 
hSBA GMTs for each of the ACWY test strains at Visit 11, in Groups 1 and 3 separately.
 
Proportion of subjects who achieve the 5 MenB endpoints at Visit 11, in Groups 1 and 3 combined.
 
Proportions of subjects with hSBA titers <math>\geq 1:4</math>, <math>\geq 1:8</math>, <math>\geq 1:16</math>, <math>\geq 1:32</math>, <math>\geq 1:64</math>, and <math>\geq 1:128</math> for each of the 4 primary MenB test strains at Visit 11, in Groups 1 and 3 combined.
 
hSBA GMTs for each of the 4 primary MenB test strains at Visit 11, in Groups 1 and 3 combined.
 

Objective	Endpoint

 
To further describe the immune response induced by bivalent rLP2086, as measured by hSBA performed with 4 primary MenB test strains, 2 expressing an LP2086 subfamily A protein and 2 expressing an LP2086 subfamily B protein, measured 1 month after the booster vaccination in Groups 2 and 4.
 
	
 
Proportion of subjects who achieve the 5 MenB endpoints 1 month after the booster vaccination, in Groups 2 and 4 combined.
 
Proportions of subjects with hSBA titers <math>\geq 1:4</math>, <math>\geq 1:8</math>, <math>\geq 1:16</math>, <math>\geq 1:32</math>, <math>\geq 1:64</math>, and <math>\geq 1:128</math> for each of the 4 primary MenB test strains at Visit 11, in Groups 2 and 4 combined.
 
hSBA GMTs for each of the 4 primary MenB test strains at Visit 11, in Groups 2 and 4 combined.
 

The endpoints related to the exploratory objective to further describe the immune response induced by MenABCWY compared to the immune response induced by MenACWY-CRM and bivalent rLP2086, as measured by hSBA performed with ACWY test strains and 4 primary MenB test strains, 2 expressing an LP2086 subfamily A protein and 2 expressing an LP2086 subfamily B protein at blood sampling time points prior to the booster vaccination (Stage 2), are not planned to be reported.

Furthermore, for the last 2 exploratory objectives related to the further description of the immune response following the booster vaccination, the endpoints related to the proportion of subjects with titers  $\geq 1:4$ ,  $\geq 1:8$ ,  $\geq 1:16$ ,  $\geq 1:32$ ,  $\geq 1:64$ , and  $\geq 1:128$  and the endpoints related to the proportion of subjects who achieve the 5 MenB endpoints are not planned to be reported.

### 3.4. Baseline Variables

Prevaccination blood draw (Visit 1) will be performed according to the Schedule of Activities Table 4. The immunogenicity results from Visit 1 are considered the baseline results for the immunogenicity analyses during Stage 1. The prevaccination blood draw prior to the booster vaccination (Visit 10) will be considered the baseline result for the immunogenicity analyses during Stage 2.

Day 1 is defined as the day of vaccination (Visit 1, Month 0) and also the start of when local reactions and systemic events are to be reported in the e-diary.

#### 3.4.1. Demographic, Medical History, and Baseline Characteristic Variables

Demographic variables collected at Visit 1 include sex, race, ethnicity, and date of birth. Categories of race include:

- Black or African American
- American Indian or Alaska Native
- Asian

- Native Hawaiian or other Pacific Islander
- White
- Other

Ethnicity includes:

- Hispanic or Latino
- Non-Hispanic/non-Latino

For countries where the full date of birth is collected, age at the time of the first vaccination and age at randomization will be derived based on birthday. For example, if the first vaccination date is 1 day before the subject's 13th birthday, the subject is 12 years old.

Medical history will be assessed at Visit 1 and Visit 10 and categorized according to the current version (at the time of reporting) of the Medical Dictionary for Regulatory Activities (MedDRA).

Physical examination will be assessed prior to vaccination at Visit 1 and each body system examined will be recorded in the case report form (CRF) as normal, abnormal, or not done.

### **3.4.2. Previous Vaccinations**

For subjects who have received a polyribosylribitol phosphate oligosaccharide of *Haemophilus influenzae* type b conjugate to outer membrane protein (PRP-OMP) vaccine, the name of the vaccine (PedvaxHIB and Comvax/Procomvax) and date of administration will be recorded on the CRF.

Similarly, for subjects who have received any prior meningococcal vaccines or vaccines containing 1 or more ACWY groups, the trade name and date of administration will be recorded on the CRF.

## **3.5. Safety Endpoints**

### **3.5.1. Adverse Events**

The relationship between (S)AEs and the investigational products will be characterized as related or not related as determined by investigators and as described in the protocol. The severity of AEs will be characterized as mild, moderate, and severe.

The time period for actively eliciting and collecting (S)AEs, MAEs, NDCMCs, and research-related injuries (RRIs) for each subject is outlined in [Table 5](#).

**Table 5. Summary of AE Collection**

	Visits 1-4	Visit 5	Visit 6	Visits 7-9	Visits 10-11	Visit 12
Approximate Month	0-7	12	12-18	18-42	54-55	60
Nonserious AEs	ICD through and including Visit 4			Within 48 hours of blood draw	From Visit 10 to Visit 11	
SAEs	ICD through and including Visit 4	Since Visit 4	Nonactive SAE collection period		From Visit 10 to Visit 11	Since Visit 11
MAEs	ICD through and including Visit 4	Since Visit 4			From Visit 10 to Visit 11	Since Visit 11
NDCMCs	ICD through and including Visit 4	Since Visit 4			From Visit 10 to Visit 11	Since Visit 11
RRIs				Within 48 hours of blood draw		

Abbreviations: ICD = informed consent document; MAE = medically attended adverse event; NDCMC = newly diagnosed chronic medical condition; RRI = research-related injury.

An MAE, which is defined as a nonserious AE that results in an evaluation at a medical facility, and the number of days subjects missed school or work because of AEs will be captured on the AE checklist (see Schedule of Activities [Table 4](#)). Neuroinflammatory and autoimmune conditions will also be captured on the AE checklist. An NDCMC is defined as a disease or medical condition not previously identified that is expected to be persistent or otherwise long-lasting in its effects.

All events are collected on the CRF and will be categorized according to the current version (at the time of reporting) of MedDRA.

An AE is considered treatment emergent relative to a given treatment if:

- the event occurs for the first time after vaccination has occurred and was not present prior to vaccination, or
- the event was present prior to vaccination but increased in severity after vaccination.

Events occurring prior to the first vaccination are not considered treatment emergent as defined here and will be excluded from the AE analyses.

### 3.5.1.1. Analysis Intervals

There will be up to 9 analysis intervals for most of the safety data collected via the CRF (Table 6).

**Table 6. Analysis Intervals for AEs, SAEs, MAEs, and NDCMCs**

No.	Analysis Interval	Analysis Population	Interval Start Date (Inclusive)	Interval Stop Date (Inclusive)	Safety Data
1	Within 30 days of Vaccination 1	Vax 1 safety	Vax 1 date	Vax 1 date + 30 days	AE, SAE, MAE, NDCMC
2	Within 30 days of Vaccination 2	Vax 2 safety	Vax 2 date	Vax 2 date + 30 days	AE, SAE, MAE, NDCMC
3	Within 30 days of any Stage 1 vaccination	Safety	Vax 1 date or Vax 2 date	Vax 1 date +30 days or Vax 2 date +30 days	AE, SAE, MAE, NDCMC
4	During Stage 1 vaccination phase	Safety	Visit 1 date	Visit 4 date	AE, SAE, MAE, NDCMC
5	During Stage 1 follow-up phase	Follow-up Stage 1	Visit 4 date +1	Visit 5 date	SAE, MAE, NDCMC
6	Throughout Stage 1	Safety	Visit 1 date	Visit 5 date	SAE, MAE, NDCMC
7	During booster vaccination phase	Booster vax safety	Visit 10 date	Visit 11 date (or end of booster vaccination day)	AE, SAE, MAE, NDCMC
8	During booster vaccination follow-up phase	Follow-up booster	Visit 11 date + 1, or end of booster vaccination date + 1 for early withdrawal subjects	Visit 12 date	SAE, MAE, NDCMC
9	Throughout booster phase	Booster safety	Visit 10 date	Visit 12 date	SAE, MAE, NDCMC

Abbreviations: MAE = medically attended adverse event; NDCMC = newly diagnosed chronic medical condition; vax = vaccination.

Three analysis intervals will be applied to immediate AEs (Table 7).

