**Table 1. Summary of Major Changes in SAP Amendments**

Version / Date	Associated Protocol Amendment	Rationale	Specific Changes
4 17MAY2021	Amendment 2, 09JUL2019	Protocol Amendment	
 
• Moved the booster dose safety endpoints from secondary to primary safety endpoints.
 
• Moved some immunogenicity endpoints (related to persistence evaluation) from secondary to exploratory endpoints.
 
• Removed the 1:4 endpoint for ACWY strains for the persistence and booster endpoints.
 
• Updated the Stage 2 enrollment, for ACWY-experienced subjects in addition to ACWY-naïve subjects to obtain data on the persistence of the immune response after 2 doses of Neisseria meningitidis group A, B, C, W, and Y vaccine (MenABCWY) as well as on the safety and immunogenicity of the booster response in individuals who had previously received an ACWY-containing vaccine.
 
• Removed the persistence and booster endpoints for defined titers; removed the persistence endpoints for geometric mean titers (GMTs).
 

5 28 Feb 2022	N/A	
Table reduction initiative, including reducing redundancy
 
Adding additional analyses
 
Administrative changes
	
 
• Removed from Stage 2 analyses the exploratory 4-fold rise and the composite response endpoint for MenB strains.
 
• Replaced some study conduct tables for Stage 2 with listings in Section 6.6.
 
• Added exploratory analyses for MenA/C/W/Y to investigate the relationship between the pre-booster dose and the post-booster dose titers in Section 6.4.
 
• Added in Section 7.1 a new planned reporting event performed when subjects have completed the 1-month postbooster blood draw.
 
• Updated the temperature scale of severity for fever for Stage 2 (Table 14) in Section 3.5.2.2 to allow for consistency in severity designation between temperatures recorded in Fahrenheit and Celsius.
 
• Added the definition of the booster safety population in Section 4.4.
 

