  - From the booster vaccination (Visit 10) through 6 months after the booster vaccination (Visit 12)
- Percentage of subjects with at least 1 AE occurring during the following time periods:
  - During the booster vaccination phase (from the booster vaccination [Visit 10] through 1 month after the booster vaccination [Visit 11]).
- Percentage of subjects reporting at least 1 immediate AE after the booster vaccination.
- The number of days subjects missed school or work because of AEs after the booster vaccination.

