#### 4.4. Safety Analysis Set

The safety population will be used for all safety analyses and will be defined for each stage of the study.

1. The safety population for Stage 1 will include subjects who have received at least 1 dose of investigational product during Stage 1 and for whom safety data are available.
2. The safety population for Stage 2 will include subjects who received the booster vaccination and for whom safety data are available.

For the safety analysis, subjects will be analyzed according to the investigational product received.

Separate safety populations will be defined for each vaccination visit: Vaccination 1, Vaccination 2, follow-up phase for Stage 1, persistence phase, booster vaccination visit, and follow-up phase for Stage 2.

1. Vaccination 1 safety population: this population will include subjects who receive the first dose of investigational product (MenABCWY+saline or bivalent rLP2086+MenACWY-CRM) at Visit 1, and for whom safety information from Visit 1 to prior to Visit 3 is available.
2. Vaccination 2 safety population: this population will include subjects who receive the second dose of investigational product (MenABCWY or bivalent rLP2086) at Visit 3, and for whom safety information from Visit 3 up to and including Visit 4 is available.
3. Follow-up safety population for Stage 1: this population will include subjects who receive at least 1 dose of investigational product and for whom safety information is available from after Visit 4 up to and including Visit 5.
4. Persistence safety population: this population will include all subjects who signed the ICD at Visit 7. This population is analogous to the Stage 2 ITT population.
5. Booster vaccination safety population: this population will include all subjects who receive the booster dose of investigational product (MenABCWY or bivalent rLP2086) at Visit 10, and for whom safety information from Visit 10 up to and including Visit 11 is available.
6. Follow-up safety population for Stage 2: this population will include all subjects who receive the booster dose of investigational product and for whom safety information is available from after Visit 11 up to and including Visit 12.
7. Booster safety population: this population will include all subjects who receive the booster dose of investigational product at Visit 10, and for whom safety information from Visit 10 up to and including Visit 12 is available.

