The safety analysis set is the primary population for the safety endpoints.

Subjects who are withdrawn early after booster vaccination during Stage 2 will be included in the follow-up safety population for Stage 2, in case they have any type of AEs in the booster vaccination follow-up interval.

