#### **6.2.2.3. Adverse Events**

Descriptive summary reports will be generated for AEs reported during the Stage 1 and booster vaccination phases (analysis intervals 1, 2, 3, 4, and 7 in [Table 6](#)) and will be similarly displayed as the summary output described in [Section 6.1.2.3](#).

The differences in subjects in each vaccine group (Group 1 – Group 3) reporting at least 1 AE during the Stage 1 vaccination phase may be summarized. The corresponding 95% CIs will also be computed using the Miettinen-Nurminen method.

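### As written, SAP Table 6 ends the booster AE interval on the vaccination day for subjects without Visit 11, so their later recorded plain nonserious AEs are listed but not counted in a primary safety endpoint

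*SAP*

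**What the plan says.** SAP Section 3.1.2 makes the percentage of subjects with at least 1 AE a primary safety endpoint for the booster, over this window: "During the booster vaccination phase (from the booster vaccination [Visit 10] through 1 month after the booster vaccination [Visit 11"]). The SAP change history confirms the status: "Moved the booster dose safety endpoints from secondary to primary safety endpoints".

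SAP Table 6 has three booster intervals:

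- **Interval 7** (vaccination phase) summarises AEs, SAEs, MAEs and NDCMCs. It starts at Visit 10 and stops at "Visit 11 date (or end of booster vaccination day").
- **Interval 8** (follow-up) summarises SAEs, MAEs and NDCMCs only. It starts at "Visit 11 date + 1, or end of booster vaccination date + 1 for early withdrawal subjects".
- **Interval 9**, "Throughout booster phase", runs from Visit 10 to Visit 12 and also summarises SAEs, MAEs and NDCMCs only.

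SAP Section 6.2.2.3 restricts AE summaries to "analysis intervals 1, 2, 3, 4, and 7 in" Table 6. SAP Section 6.1.2.3 sends other nonserious AEs recorded in a follow-up phase to the overall AE listing. SAP Section 4.4 puts subjects who withdraw early after the booster into the Stage 2 follow-up safety population "in case they have any type of AEs in the booster vaccination follow-up interval". The same section defines the booster vaccination safety population, used for interval 7, as boosted subjects "for whom safety information from Visit 10 up to and including Visit 11 is available".

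**The concern.** The endpoint covers about a month. For a subject without Visit 11, the interval that implements it covers one calendar day. Rows 7 and 8 have matching cut-offs (the booster day, then the next day), so a programmer following the table would build exactly that.

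Stage 1 has a backstop. Intervals 1 to 3 run to a fixed 30 days after vaccination, so a subject who misses Visit 4 still contributes a 30-day AE window. The booster has no fixed-length interval.

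Protocol Section 6.5 names AEs among the reasons for withdrawal, so the subjects affected may not be a random sample. At stake is a descriptive primary percentage that could be slightly too low, and a split between vaccination phase and follow-up that differs from the endpoint definitions.

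**Working it through.** **1. Trace through Table 6.** Take a boosted subject with no Visit 11 and an event starting on the day after the booster or later.

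| Event | Interval 7 | Interval 8 | Interval 9 | Counted in the primary AE endpoint? |
|---|---|---|---|---|
| Plain nonserious AE | no, interval has stopped | type not summarised | type not summarised | no; listing only |
| Nonserious MAE or NDCMC | no | yes | yes | no |
| SAE | no | yes | yes | no |

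**2. Window length.** The Visit 11 window is 28 to 42 days after Visit 10 (SAP Table 4). Counting both end dates, a subject with Visit 11 contributes 28 + 1 = 29 to 42 + 1 = 43 days. The fallback gives 1 day.

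**3. What is unaffected.** Solicited reactions (SAP Table 8) and immediate AEs (SAP Table 7) are timed from the vaccination, not from Visit 11.

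**4. Denominator.** A fallback stop date in row 7 has a purpose only if subjects without Visit 11 are in that analysis. Yet the interval 7 population asks for safety information up to and including Visit 11, and the text does not say whether partial information is enough. SAP Section 6.1.2 also refers to the booster safety population for these endpoints, whose definition runs to Visit 12. Inclusion is implied but not stated.

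**5. Size.** The plan gives no figure to reproduce. Inputs:

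- N = 394 Stage 2 subjects (Protocol Section 3.3; 2 × 132 + 2 × 65 = 394). This is a participation target, not a count of boosted subjects.
- f = share of boosted subjects without Visit 11. Not given; assumed 1% to 3%.
- p = true proportion with at least 1 AE in the booster phase. Not given; assumed 10% to 30%, with constant daily risk over 30 days.
- All AEs are captured, and these subjects are in the denominator (assumed).

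Probability of an AE on the booster day: p1 = 1 − (1 − p)^(1/30). Subjects lost from the numerator: N × f × (p − p1). Fall in the percentage: 100 × f × (p − p1).

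| f | p | p1 | Subjects lost | Points |
|---|---|---|---|---|
| 1% | 10% | 0.0035 | 394 × 0.01 × 0.0965 = 0.4 | 0.1 |
| 3% | 20% | 0.0074 | 394 × 0.03 × 0.1926 = 2.3 | 0.6 |
| 3% | 30% | 0.0118 | 394 × 0.03 × 0.2882 = 3.4 | 0.9 |

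Within a single group, each lost case lowers the percentage by 100/65 = 1.5 points (Group 2 or 4) or 100/132 = 0.8 points (Group 1 or 3).

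**The case against.** The strongest reply is that row 8's wording can be read as the date on which the booster vaccination phase ended for a withdrawn subject. Row 7 is labelled as a phase, SAP Section 6.6.1 treats Visits 10 to 11 as one, and elsewhere the SAP names the injection day more simply. On that reading AEs up to withdrawal stay in interval 7 and the loss disappears. The sentence in Section 4.4 gives no start date for the follow-up interval, so it fits both readings. The phase reading is possible, but it is not written and row 7's word for a day goes against it. If it is what was meant, Table 6 should say so.

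Three further replies stand in part:

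- **The events are not lost from the report.** They reach the AE listing. Related AEs will be summarised by stage and severe AEs may be (SAP 6.7.2.1, 6.7.2.2), AEs leading to withdrawal may be listed (6.7.2.5), and SAEs, MAEs and NDCMCs remain in interval 9. None of this restores the primary percentage.
- **Few such events may be recorded.** Plain AEs are actively collected from Visit 10 to Visit 11, and the Visit 12 call asks only about SAEs, NDCMCs and medically attended AEs (Protocol 8.1.4). A new stop date cannot recover what was never elicited. But Protocol 6.5 asks for every attempt to collect AEs after each vaccination and, when possible, for next-visit procedures at withdrawal. So some data can exist, and the group without a Visit 11 should be small.
- **No decision depends on it.** SAP 5.2.1.3 says the safety intervals will not be used to test hypotheses.

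A reader might infer that every subject without Visit 11 is a lost AE case. With 1–3% of 394 that would be about 4 to 12 subjects. The documents do not support this: a loss also needs a recorded AE after the booster day and none on it.

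**Conclusion.** The rule is wrong as literally written: for boosted subjects without Visit 11 it does not deliver the window that the primary AE endpoint defines. Recorded plain nonserious AEs after the booster day are listed but not counted, and SAEs, MAEs and NDCMCs shift from the vaccination phase to follow-up.

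It would go too far to conclude that the primary percentage is certainly under-counted. That follows only if these subjects are in the interval 7 denominator, which is implied but not settled. If they are excluded, the percentage is not diluted, but all their events leave the vaccination-phase analysis.

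The effect is probably small: about 0.4 to 3.4 of 394 subjects, or 0.1 to 0.9 points, on the assumed 1–3% without Visit 11 and 10–30% with an AE, and less where AEs were not elicited. The true size cannot be derived from the documents. The point should be corrected because the text conflicts with the endpoint and the repair is cheap; it does not threaten the study's conclusions.

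**What to change.** In SAP Table 6, for any boosted subject without Visit 11, whether withdrawn or still in the study:

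- Set the interval 7 stop date to the earlier of the last contact and booster date + 42 days, the top of the Visit 11 window. Booster date + 30 days is an alternative that would match intervals 1 to 3.
- Start interval 8 on the following day. Row 8 now covers early withdrawals only, so a subject who misses Visit 11 but stays in the study has no clear rule.
- State in Section 4.4 that these subjects are in the interval 7 denominator, and make Section 6.1.2 name the same population.

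The cost is two cells in Table 6, a sentence or two of text and the matching program code. No data collection changes. It should be settled before the postbooster reporting event in SAP Section 7.1.
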